8.4 Demographics

The following demographic information will be collected:

Age, Gender, Race, Ethnicity

8.5 Medical History

Record all past and/or concomitant medical conditions, diagnoses and surgeries.

8.6 Concomitant Medications

All concomitant medications (including start/stop dates and indication) must be recorded from the start of treatment through the study treatment follow-up period. Blood-thinning agents as well as any herbal supplements will be recorded.

8.7 Laboratory Assessments

Lab studies may be performed per local Standard of Care. Labs may include Albumin, Alkaline Phosphatase, ALT/SGPT, AST/SGOT, Total Bilirubin, Direct Bilirubin, Indirect Bilirubin, Lipase, Total Protein, Platelets, INR, Hepatitis Panel, Fibroscan and Fibrosure. No labs will be required for the sole purpose of this research study. The most recent lab results will be reported to the sponsor for study purposes.

For female patients of child bearing potential, pregnancy tests will be performed per local Standard of Care.

8.8 Randomization

Subjects will undergo a liver biopsy consisting of two passes using one of 2 methods: "modified wet suction" (Arm 1) and "slow pull" (Arm 2). Subjects in each of the two specimen processing groups will be randomized into each arm in a balanced manner to either the "modified wet suction" technique (ARM 1), or the "slow pull" technique (ARM2) when performing liver biopsy according to a predetermined randomization. Randomization will be stratified by site, with a block size of 4.

A numbered, sealed envelope will be utilized to identify randomization of each subject; these will be provided by study sponsor. A sheet of paper inside the envelope will indicate either ARM 1 –

Modified Wet Suction technique or ARM 2– Slow Pull technique. The envelope may be opened after the Informed Consent and Eligibility Checklists are completed. Often the Randomization envelope will be opened once the patient is in the procedure room.

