5.0 Selection of Patients

Candidates for this study are patients who will be undergoing liver biopsy under EUS guidance and are deemed to have clinical need for liver biopsy for non-malignant processes.

All patients determined by the physician to be clinically in need of a liver biopsy via EUS may be approached for possible enrollment. Usually these are patients requiring an upper endoscopy and a liver biopsy as part of workup for liver disease.

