8.9 EUS Guided Liver Biopsy

Upper endoscopy is performed with necessary biopsies or upper dilation completed if needed. Patients with evidence of significant upper gastrointestinal bleeding prior to endoscopy are exempt.

Once upper endoscopy is completed, the upper endoscope will be removed, and the Linear Array EUS scope is introduced per os. Diagnostic EUS examination is completed. EUS requiring pancreatic biopsies or interventions are exempt (See section 6). The patient is randomized to one of 2 techniques. The study will use block randomization stratified per site. The Randomization envelope is opened and the endoscopist is told which EUS guided liver biopsy technique is to be used.

Each technique will be used to perform 2 passes. A “pass” is defined as entry into the liver and then removal of tissue. An “actuation” is defined as a to and fro movement once the needle is within the liver.

An attempt to biopsy both left and right lobes of the liver will be made. If this cannot be completed for technical reasons, then the endoscopist will make a note and perform 2 passes to the lobe which is able to be biopsied.

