11.0 Sample Size

12.0 With a sample size of 72 subjects per group completing the study, 144 total subjects, the study will have 80% power to detect a 20% difference in means between the groups for the length of tracts and number of tracts, assuming two-sided tests of means using ratios, each conducted at a 5% significance level, and a coefficient of variation of 0.4. To account for up to 10% dropouts and lost samples, the study will enroll 80 subjects per group, 160 total subjects. Sample size calculations were made using PASS 13 (NCSS, Kaysville, UT). Statistical Analysis Plan

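### Allocation concealment is incomplete: with a single, printed block size of 4 within site and unblinded endoscopists, up to about a third of allocations can be deduced in advance

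*Combined protocol and SAP*

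**What the plan says.** Section 8.8 sets the scheme: "Randomization will be stratified by site, with a block size of 4". Section 8.9 repeats that "The study will use block randomization stratified per site". No second block size is given, and nothing says that the size is withheld from sites.

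The ratio is 1:1, since section 11.0 says that "the study will enroll 80 subjects per group, 160 total subjects". A 2:2 split within each block of 4 is inferred from this.

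On concealment, section 8.8 provides that "A numbered, sealed envelope will be utilized to identify randomization of each subject; these will be provided by study sponsor", and that "The envelope may be opened after the Informed Consent and Eligibility Checklists are completed". Section 8.9 places the opening after the diagnostic EUS.

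The operator is not blinded: "The Randomization envelope is opened and the endoscopist is told which EUS guided liver biopsy technique is to be used". The pathologist is blinded to technique (section 8.15). Recruitment is discretionary: "All patients determined by the physician to be clinically in need of a liver biopsy via EUS may be approached for possible enrollment" (section 5.0).

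Section 8.8 also says: "Subjects in each of the two specimen processing groups will be randomized into each arm in a balanced manner". The sentence on stratification names only site, so it is unclear whether each processing group has its own list.

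**The concern.** Concealment has two parts: nobody should be able to read the next allocation, and nobody should be able to infer it. The envelopes deal with the first. A known, fixed block size weakens the second when past allocations are visible at the site, as they are here. The endoscopist signs the protocol (section 18.5), the site keeps it on file (section 14.1), and every allocation is acted on in the procedure room.

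Once a block boundary is known, the fourth allocation in a block is certain, and so is the third if the first two match. A physician who knows the next technique could approach, defer or pass over a patient accordingly. Specimen length, fragmentation and portal tract count may depend on the liver as well as the technique, so such selection could make the arms differ before sampling.

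The rest of the plan would not readily expose or correct this. An eligibility form is required for consented subjects (section 14.0), and no screening log is described for those not approached. The models in section 12.3 adjust for site, endoscopist, side and processing, but for no baseline patient or liver characteristic. Pathologist blinding protects the reading of specimens, not the make-up of the arms.

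**Working it through.** **The plan's own figures.** The documents give no figure for predictability. The sample size, used in the last step, does reproduce. With CV 0.4 the log-scale SD is √ln(1 + 0.4²) = 0.385, and the target is ln(1.2) = 0.182. The noncentral t calculation gives 72 per group (power 80.5%), and 72/0.9 = 80 enrolled per group. This has no bearing on concealment.

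**Certain allocations, complete blocks.** A 2:2 block of 4 has 6 equally likely sequences. The chance that a position is fixed by those before it is:
- positions 1 and 2: 0
- position 3: 1/3 (when the first two match)
- position 4: 1

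The share is (0 + 0 + 1/3 + 1)/4 = 33.3%, or at most 160/3 ≈ 53 of 160 subjects.

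**Best guess.** Always guessing the arm that lags is right with probability (0.5 + 0.667 + 0.667 + 1)/4 = 70.8%, against 50% by chance.

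**Unfinished blocks.** With one list per site and m subjects, the share is the sum of the position probabilities divided by m:
- m = 6: (4/3)/6 = 22%
- m = 7: (4/3 + 1/3)/7 = 24%
- m = 10: (8/3)/10 = 27%
- m a multiple of 4: 33%

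A site with 3 subjects has 11%, and one with 1 or 2 has none. Section 4.0 allows up to 20 sites, a mean of 160/20 = 8 subjects. Simulating 160 subjects over an assumed 5, 10 or 20 sites gives about 32%, 31% and 28% overall, so about 45 to 51 subjects (0.28 × 160 and 0.32 × 160). If each processing group had its own list, it would be about 31% with 5 sites and 23–25% with 20.

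**Mixed blocks of 4 and 6, sizes equally likely.** A tracker who relies only on the running imbalance is certain when it reaches 3. That occurs in 2 of the 20 sequences of a block of 6, so 0.1 times per 10 allocations, or 1%. A tracker who also knows the set of sizes and follows the list from its start is certain for about 6% (simulation). Best-guess success over complete blocks is (4 × 0.708 + 6 × 0.683)/10 = 69%. Over a list of only 8 subjects it is about 67%.

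**Illustration of consequence.** Take 72 per arm and one value per subject, so the SE of the log ratio is 0.385 × √(2/72) = 0.064. If selection alone shifted the ratio of means by 2.5%, 5% or 10%, the two-sided 5% test would reject a true null about 6.7%, 11.8% or 31.7% of the time. These shifts are assumptions. If steering acted only on the certain third, a 5% shift would need the patients steered to the two arms to differ in expected yield by 1.05³ − 1 = 16%, and a 10% shift by 1.10³ − 1 = 33%.

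**The case against.** A reader might infer that allocation is not concealed at all, or that the comparison is biased. The documents support neither. Numbered, sealed envelopes come from the sponsor and are opened only after consent and the eligibility check, and at least two thirds of allocations remain uncertain.

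One third is also a ceiling. It needs complete blocks and someone who sees every earlier allocation and knows the block boundaries. The separate random effect for endoscopist in section 12.3 suggests several operators at some sites, and one of them may not see colleagues' cases. Consent belongs to screening and randomisation to the procedure day (section 7.0), so with several consented patients waiting, a patient's place in the list may not be fixed when the patient is approached. Biopsy must be clinically indicated, which limits deferral.

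Steering would have to favour the same technique across sites, or it would cancel. Section 2.0 describes both techniques as widely accepted, and nothing shows that operators can predict yield well. The 10% illustration needs a 33% difference among steered patients, more than the 20% effect for which the trial is powered.

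All of this stands, and it limits the size of the problem. It does not remove it. The opening rule protects the contents of the envelope, whereas a deduced allocation can be known before the patient is approached. On the procedure day the diagnostic EUS precedes opening, so an operator who has deduced the arm has also seen the liver.

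It is also fair to say that mixed blocks barely change best-guess success. Their gain is in removing near-certain knowledge.

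**Conclusion.** The point holds in limited form. At a site where someone tracks the full sequence, up to about one third of allocations can be deduced with certainty in advance. The range is roughly 22–33%, depending on subjects per site and list structure, and it is lower at sites with fewer than four subjects. This assumes a 2:2 split in each block and full sight of the site's earlier allocations.

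The documents do not show that steering occurred, so the type I error figures illustrate a mechanism and do not estimate this trial's error rate. The weakness is worth correcting because the operator is unblinded, the remedy is cheap, and no described safeguard would reveal selective approach.

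**What to change.** For envelopes not yet used, generate new lists, still stratified by site, with randomly varying block sizes (for example 4 and 6). Delete the block size from section 8.8 and say there only that randomly permuted blocks of varying size, undisclosed to sites, are used. Hold the sizes in a restricted randomisation document.

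The cost is a new list, replacement envelopes and a short amendment to section 8.8. Eligibility, procedures, endpoints and sample size are untouched. Within-site imbalance could be slightly larger, mainly at sites with few subjects.

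The change does nothing for subjects already randomised. Section 12.3 refers to the small number of subjects with mesh prep, which suggests that enrolment had begun, and the share still to be randomised is not stated. For those already allocated, the report should state the fixed, disclosed block size of 4 as a limitation.

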8.9 EUS Guided Liver Biopsy

Upper endoscopy is performed with necessary biopsies or upper dilation completed if needed. Patients with evidence of significant upper gastrointestinal bleeding prior to endoscopy are exempt.

Once upper endoscopy is completed, the upper endoscope will be removed, and the Linear Array EUS scope is introduced per os. Diagnostic EUS examination is completed. EUS requiring pancreatic biopsies or interventions are exempt (See section 6). The patient is randomized to one of 2 techniques. The study will use block randomization stratified per site. The Randomization envelope is opened and the endoscopist is told which EUS guided liver biopsy technique is to be used.

Each technique will be used to perform 2 passes. A “pass” is defined as entry into the liver and then removal of tissue. An “actuation” is defined as a to and fro movement once the needle is within the liver.

An attempt to biopsy both left and right lobes of the liver will be made. If this cannot be completed for technical reasons, then the endoscopist will make a note and perform 2 passes to the lobe which is able to be biopsied.

8.10 Arm 1- “Modified Wet suction”

The right or left lobe of the liver is initially targeted.

Doppler and EUS imaging are used to avoid significant vessels and large ducts when identifying appropriate biopsy tract.

The stylet is removed from the onset of the procedure. It will only be used to push the specimen out of the needle. A syringe is used to flush the needle with 5 cc of saline. Then a syringe that contains 3cc of saline with preloaded 20cc of suction with the valve in the off position is attached to the back of a 19g Acquire Boston Scientific needle. The needle is advanced into the liver just beyond the capsule. An initial pass of at least 4-5 cm is made into the liver with a quick forceful forward movement, the needle is then slowly pulled back to the edge of the capsule. The valve is switched to the open position. 2-4 actuations are made driving the needle at least 4-5 cm in length every time while the angle is changes slightly (1-3mm) with each actuation. No fanning. The needle is then pulled out of the liver with the valve switched to the closed position just prior to removing the needle from the liver. Often a flash of blood may be seen. The needle is removed and the specimen is taken for processing (see processing below).

The endoscopist then finds a second site to biopsy within the other lobe. If it is deemed by the endoscopist to not be able to biopsy the other lobe for technical reasons, this will be noted and tracked and an additional tract will be biopsied within the same lobe. Again, taking care to avoid vessels and large bile ducts, a second pass is made with the same technique.

In the event that a pass returns with no or inadequate tissue, the endoscopist will switch to the opposite technique and proceed as per protocol.

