8.11 Arm 2- “Slow Pull”

The right or left lobe of the liver is initially targeted.

Doppler and EUS imaging are used to avoid significant vessels and large ducts when identifying appropriate biopsy tract.

The stylet is maintained from the onset of the procedure. It will later be used to push specimen through the needle. Using the 19g Acquire Boston Scientific needle, the needle is advanced into the liver just beyond the capsule. No fanning. The stylet is pulled back about 2cm. The needle is passed at least 4-5 cm into the liver with a quick forceful forward movement, as it is slowly withdrawn the nurse pulls back the stylet part with each withdrawal after actuation. This is repeated 2-4 times while the angle is changed slightly (1-3mm) with each actuation. The end the stylet is almost but not completely withdrawn from the needle. The needle is then pulled out of the liver. The needle is removed. The specimen is then taken for processing (see processing below).

The endoscopist then finds a second site to biopsy within the other lobe. If it is deemed by the endoscopist to not be able to biopsy the other lobe for technical reasons, this will be noted and tracked and an additional tract will be biopsied within the same lobe. Again, taking care to avoid vessels and large bile ducts, a second pass is made with the same technique.

In the event that a pass returns with no or inadequate tissue, the endoscopist will switch to the opposite technique and proceed as per protocol.

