8.16 Post Biopsy CRF

A summary of lobes biopsied, pathology findings, EUS findings and EGD findings.

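### Do the two arm descriptions give modified wet suction an extra needle stroke per pass, and so bias the comparison of yield?

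*Combined protocol and SAP*

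**What the plan says.** In Section 8.9 an actuation "is defined as a to and fro movement once the needle is within the liver", while a pass is one entry into the liver ending with retrieval of tissue. Each subject has two passes.

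- **Arm 1 (Section 8.10).** "An initial pass of at least 4-5 cm is made into the liver with a quick forceful forward movement"; then "the needle is then slowly pulled back to the edge of the capsule". Only after that comes "The valve is switched to the open position", followed by "2-4 actuations are made driving the needle at least 4-5 cm in length every time".
- **Arm 2 (Section 8.11).** "The needle is passed at least 4-5 cm into the liver with a quick forceful forward movement". The needle is drawn back slowly while the nurse retracts the stylet, and "This is repeated 2-4 times while the angle is changed slightly (1-3mm) with each actuation".

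The endoscopist learns the arm when the envelope is opened (Section 8.9). The pathologist stays blinded (Section 8.15). Section 8.16 gives the content of the post-biopsy form in one line: "A summary of lobes biopsied, pathology findings, EUS findings and EGD findings". The models in Section 12.3 have terms for technique, site, endoscopist, subject, side and sample processing, but none for stroke count.

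**The concern.** Arm 1's opening movement goes forward and back inside the liver, so it meets Section 8.9's definition of an actuation although Section 8.10 does not count it as one. Adding it gives 3-5 strokes. If Arm 2's 2-4 is a total, the arms compare as 3 to 2, 4 to 3 or 5 to 4, which is 50%, 33% or 25% more strokes in Arm 1. Each exceeds the 20% difference that the trial is sized to detect. In both arms the operator also picks a number within a twofold range after learning the allocation, and the text mentions no record of the choice.

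More strokes could plausibly bring more tissue. A gain in specimen length or portal tracts might then be credited to suction when it came from extra needle movements, and without a recorded count nobody could separate the two.

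**Working it through.** **1. The plan's own figure.** Inputs from Section 11.0: coefficient of variation 0.4, 20% difference tested as a ratio, two-sided 5%, 80% power.

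- Log-scale SD = √ln(1 + 0.4²) = 0.3853; target = ln 1.20 = 0.1823.
- Normal approximation: 70.1, so 71 per group. Noncentral t: 72 per group, with power 80.5%.
- 72 / 0.90 = 80 per group, 160 in total.

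The stated 72 and 80 reproduce, so the same test can be used below.

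**2. Strokes per pass.**

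| Reading of Section 8.11 | Arm 1 | Arm 2 | Ratio at equal operator choice |
|---|---|---|---|
| One stroke, then 2-4 repeats (literal) | 1 + (2-4) = 3-5 | 1 + (2-4) = 3-5 | 1.00 |
| 2-4 strokes in total | 3-5 | 2-4 | 1.50, 1.33 or 1.25 |

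The imbalance exists only on the second row.

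**3. What the second row would do to yield.** The documents give no yield per stroke. Assume yield is proportional to strokes^e, with e from 0 (no dependence) to 1 (proportional). The spurious yield ratio is then (stroke ratio)^e. It reaches 1.20 when e = ln 1.20 / ln(stroke ratio), which is 0.45 for 3:2, 0.63 for 4:3 and 0.82 for 5:4. With no true technique effect, 72 per group and one analysed value per subject, the noncentrality is e × ln(stroke ratio) / (0.3853 × √(2/72)). The chance of p < 0.05 is:

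| e | 3:2 | 4:3 | 5:4 |
|---|---|---|---|
| 0 | 5% | 5% | 5% |
| 0.25 | 34.8% | 19.9% | 13.9% |
| 0.5 | 88.0% | 60.5% | 40.8% |
| 1 | about 100% | 99.4% | 93.2% |

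The whole span is set by e, which is unknown here.

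**4. The extra stroke has no suction.** In Section 8.10 the valve opens only after the first stroke has been withdrawn, so Arm 1 has 2-4 strokes under suction. Suppose the valve-off stroke yields a fraction f of a suction stroke, k suction strokes follow, an Arm 2 stroke yields as much as a suction stroke, and yield is otherwise proportional. On the second row the ratio is then (k + f)/k, which reaches 1.20 only when f = 0.2k: 0.4, 0.6 or 0.8 for k = 2, 3 or 4. With f = 0 the ratio is 1.00 even on the unfavourable reading.

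**5. Operator choice.** Both arms carry the same 2-4 range. Choice unrelated to arm adds spread, not bias. Bias needs average counts that differ by arm: under proportionality and a mean of 3 strokes, by 0.2 × 3 = 0.6. Individual pairs such as 4 v 3 (ratio 1.33) or 5 v 3 (1.67) can favour either arm. Nothing in the documents suggests that operators would choose differently by arm.

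**6. The record.** The line in Section 8.16 also omits total EUS time, liver biopsy time and recovery time, although Sections 8.12, 8.13 and 8.18 define them and Section 12.3 analyses them. It is therefore not a full list of collected items. The case report forms themselves are not in the documents, so absence of the count from that line does not show that it goes unrecorded.

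**The case for a change.** The strongest case for acting does not need the unequal reading. Up to 20 sites (Section 4.0) may each read Section 8.11 in their own way. The operator is unblinded on either reading. Random effects for site and endoscopist do not absorb an endoscopist who uses different counts in the two arms. Section 2.0 rests the rationale on the stronger pull of a saline column, so a difference caused by stroke number would be credited to the wrong mechanism. Because the count arises after randomisation, adjusting for it later would not fully repair the attribution. A clarification and one form entry per pass would be cheap.

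Much of this stands as description. The wording is ambiguous, Section 8.10 calls its first stroke a pass in a sense that Section 8.9 does not allow, and the text describes no count. It does not show that a planned result would be wrong. Sections 1.0 and 3.1 set out to compare two named techniques, and the valve-off first stroke is a written step of one of them. Stroke count is part of what is delivered, so randomisation protects that comparison; only the mechanistic explanation is exposed. The direction is also unclear for the full primary endpoint: Section 12.1 includes fragmentation as well as length and portal tracts, and nothing says how more strokes would affect it. Having operators commit to a number before allocation would restrict procedural discretion to prevent an arm-specific habit that nobody has shown. That is a debatable trade-off, not a correction.

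**Conclusion.** The concern does not hold as a fault in the design or analysis. A one-stroke excess in Arm 1 follows only if Section 8.11's range is a total; on the literal reading both arms have 3-5 strokes and the built-in bias is nil. On the other reading, with 4 strokes against 3, the chance of a spurious significant result lies anywhere from 5% to 99%, depending on a yield per stroke that the documents do not give and on the valve-off stroke counting as much as a suction stroke. The comparison of techniques as delivered is valid throughout; what could suffer is attribution of a difference to suction.

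What remains is clerical. Sections 8.9, 8.10 and 8.11 must be reconciled on how strokes are counted, and which count is intended is for the sponsor to say. A study team would settle this in site instructions and could report the count by arm as description. Neither step alters an endpoint, a model or the 72 per group. This rests on two assumptions: operators do not choose systematically different counts by arm, and the trial's question is the one in Section 3.1 and not the mechanism in Section 2.0.
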